3.1.3.2. Part C: Expansion Cohort

Expansion cohorts may be opened at any dose level that has cleared DLT evaluation. Up to approximately 60 patients will be enrolled in expansion cohorts.

The totality of data from all patients in dose escalation and expansion will be used to determine the recommended q1wk LV dose. After the q1wk dose has been determined, additional patients may be enrolled at the recommended dose.

3.1.4. Part D: Day 1 and Day 8 every 21-days LV dosing

Part D will assess LV 1.5 mg/kg administered on Day 1 and Day 8 (off Day 15) of every 21-day cycle, not to exceed 200 mg per infusion, in combination with pembrolizumab administered on Day 1 of every cycle. Approximately 40 patients with PD-L1 CPS<10 will be enrolled in Part D. Ongoing, real-time, continuous review of patient safety and SAEs will be conducted by the sponsor's Drug Safety Department. Additionally, the ISMC will ensure periodic safety data review throughout the study.

a Dose will be de-escalated if the first 2 DLT-evaluable patients in a dose level experience a DLT. Further evaluation of that dose level may be allowed if recommended by the SMC.

3.1.5. Dose-Limiting Toxicity

DLTs are only assessed during Part A and dose escalation cohorts in Part C of the study.

The DLT-evaluation period is the first treatment cycle in Part A and Part C dose escalation. Patients who experience a DLT in Cycle 1 should not receive further treatment with LV and pembrolizumab, unless clinical benefit is demonstrated with adequately managed toxicity. Subsequent doses will be defined by the medical monitor in discussion with the site investigator, in the context of the type of AE observed.

The IBs for LV and pembrolizumab individually describe AEs commonly observed relative to either agent, as well as less common serious findings. The respective IBs should be referenced when attributing causality; however, the final decision regarding causality is at the discretion of the investigator.

If any patient enrolled in Part A or Part C dose escalation discontinues the study without DLT during the DLT period, another patient may be enrolled at the same dose level for DLT evaluation. However, the original patient will be included in the safety analysis.

No DLT evaluation will be conducted in Part D, because no DLT was observed with LV 1.5 mg/kg weekly dosing in SGNLVA-001 (see Section 3.2.3.4). Furthermore, pharmacokinetic exposure of LV given 1.5 mg/kg on Days 1 and 8 every 3 weeks will not surpass LV given 1.5 mg/kg weekly.

3.1.5.1. Dose-Limiting Toxicity in Part A

A DLT in Part A is defined as 1 of the following that is considered related to LV or the combination, and cannot be attributed to pembrolizumab alone:

- Any clinically significant, non-hematologic AE ≥ Grade 3 according to the National Cancer Institute Common Terminology Criteria for Adverse Events (NCI CTCAE), Version 4.03 (exceptions noted in list below)
- ≥ Grade 3 febrile neutropenia
- Grade 4 thrombocytopenia or Grade 3 thrombocytopenia associated with clinically significant bleeding that requires medical intervention
- Grade 4 anemia unrelated to underlying disease
- Discontinuation during Cycle 1 due to treatment-related toxicity
- Prolonged delay (>2 weeks) in initiating Cycle 2 due to treatment-related toxicity
- Grade 5 event (death)

The following events will not be considered a DLT:

- Grade 3 fatigue that improves to ≤ Grade 1 within 3 days with or without medical assessment
- Grade 3 tumor pain that improves to ≤ Grade 1 within 3 days with or without medical assessment

- LV infusion: Grade 3 infusion-related reactions (IRRs) that resolve within 1 day with or without medical assessment
- ≥ Grade 3 non-hematological laboratory abnormalities that resolve to ≤ Grade 1 within 7 days with or without optimal medical management
- Isolated Grade 3 or 4 electrolyte imbalances/abnormalities and Grade 3 elevations in blood glucose not associated with clinical sequelae that are corrected with supplementation/appropriate management within 3 days
- Grade 3 rash that improves to ≤ Grade 2 within 3 days with or without medical assessment
- Grade 3 nausea that improves to ≤ Grade 1 within 3 days with or without medical assessment
- Grade 3 diarrhea that improves to ≤ Grade 1 within 3 days with or without medical assessment
- Grade 3 vomiting that improves to ≤ Grade 1 within 3 days with or without medical assessment

The following event will not be considered DLT evaluable:

 Pembrolizumab infusion: ≥ Grade 3 IRRs – these patients must be discontinued from pembrolizumab (see Sections 5.3.5, 9.3.1.7), and are not evaluable for DLTs.

3.1.5.2. Dose-Limiting Toxicity in Part C

A DLT in Part C is defined as 1 of the following that is considered related to LV or the combination, and cannot be attributed to pembrolizumab alone:

- Any clinically significant, non-hematologic AE ≥ Grade 3 according to the NCI CTCAE, Version 4.03 (exceptions noted in list below)
- Strade 3 febrile neutropenia
- Grade 4 thrombocytopenia or Grade 3 thrombocytopenia associated with clinically significant bleeding that requires medical intervention
- Grade 4 anemia unrelated to underlying disease
- Discontinuation during Cycle 1 due to treatment-related toxicity
- Inability to receive all 3 doses of LV (Days 1, 8, and 15) due to patient not meeting dosing criteria (see Section 5.2.3.5)
- Prolonged delay (>2 weeks) in initiating Cycle 2 due to treatment-related toxicity
- Grade 5 event (death)

The following events will not be considered a DLT:

- Grade 3 fatigue that improves to ≤ Grade 1 within 3 days with or without medical assessment
- Grade 3 tumor pain that improves to ≤ Grade 1 within 3 days with or without medical assessment

- LV infusion: Grade 3 IRRs that resolve within 1 day with or without medical assessment
- ≥ Grade 3 non-hematological laboratory abnormalities that resolve to ≤ Grade 1 within
 7 days with or without optimal medical management
- Isolated Grade 3 or 4 electrolyte imbalances/abnormalities and Grade 3 elevations in blood glucose not associated with clinical sequelae that are corrected with supplementation/appropriate management within 3 days
- Grade 3 rash that improves to ≤ Grade 2 within 3 days with or without medical treatment
- Grade 3 nausea, diarrhea or vomiting that improves to ≤ Grade 1 within 3 days with or without medical treatment

The following event will not be considered DLT evaluable:

 Pembrolizumab infusion: ≥ Grade 3 IRRs – these patients must be discontinued from pembrolizumab (see Sections 5.6.1.2, 5.6.1.3) and are not evaluable for DLTs.

Patients who do not complete the 21-day DLT evaluation period for reasons other than DLT will not be considered for dose-escalation decisions and/or determination of the MTD. Patients who are considered non-evaluable for dose-escalation decisions and/or MTD and will be replaced at the same dose level.

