3.1.1. Part A: Dose De-escalation

This part of the study is designed to evaluate the safety of LV administered in combination with pembrolizumab, and to identify the maximum administered dose (MAD) for Part B. Patients will receive LV 2.5 mg/kg IV (maximum weight cap per infusion at 80 kg) as a 30-minute infusion

Amendment 11: 19-Oct-2023

Page 22 of 152

followed by pembrolizumab 200 mg IV as a 30-minute infusion on Day 1 q3wk. Patients treated under Amendment 2 and later will receive LV 2.5 mg/kg (capped at 100 kg). In consultation with the sponsor, eligible patients already on treatment prior to Amendment 2, may have their maximum weight cap per infusion increased to 100 kg or remain at 80 kg, if they are receiving benefit (CR, PR, or SD). Patients receiving >200 mg LV per infusion are required to be administered prophylactic granulocyte-colony stimulating factor (G-CSF). Pembrolizumab will be administered approximately 60 to 90 minutes after infusion of LV is complete. DLTs will be assessed in the first treatment cycle, through Cycle 2 Day 1.

Blood samples for PK and immunogenicity analysis may be collected to support the study endpoints. Pharmacodynamic and exploratory biomarker studies will also be conducted on patient blood samples and tumor tissue obtained throughout the trial, including samples obtained to determine eligibility. As of protocol Amendment 11, no PK, immunogenicity, PD, or biomarker samples will be obtained after Cycle 1.

Part A of this study will enroll approximately 12–24 patients. The dose de-escalation plan for LV in this part of the study requires de-escalation in the event that the DLT rate is $\geq 1/3$ of patients given the current dose. This plan is as follows:

Initially, 6 patients will be given the starting dose of 2.5 mg/kg (capped at 80 kg prior to Amendment 2 or 100 kg under Amendment 2 and later). Enrollment will proceed as follows:

- a. If <2 of 6 patients experience DLT at 2.5 mg/kg, 6 more patients will be enrolled at the same dose level of 2.5 mg/kg.

 - If <4 of these 12 patients experience DLTs, Part B will be initiated at 2.5 mg/kg.
 - ii. If ≥4 of 12 patients experience DLTs, the dose will be de-escalated to 2.0 mg/kg and the study will proceed as described for dose de-escalation below.

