6.3.3. Treatment Period (Day 1 to 21 of each cycle)

6.3.3.1. Day 1

The following assessments have a window of -2 days. If baseline visit activities occur within 2 days prior to Day 1, the assessments do not need to be repeated.

- Pre-dose
 - Physical exam
 - Weight
 - ECOG performance status (see Appendix F)
 - Serum chemistry panel (detailed in Section 7.5.3) to be evaluated prior to infusion.
 Hold dose if blood glucose level is >250 mg/dL.
 - CBC with differential (detailed in Section 7.5.3) to be evaluated prior to infusion.
 - Pregnancy test (for patients of childbearing potential; performed locally; does not need to be repeated if performed within 3 days of Day 1)
 - Thyroid function tests (detailed in Section 7.5.3; to include TSH, T3 or free T3, and free T4). Day 1 of each odd-numbered cycle only (i.e. Cycles 1, 3, 5, 7, etc.)

The following procedures must be performed on Day 1:

- Vital signs (within 60 minutes prior to LV infusion, within 60 minutes prior to pembrolizumab infusion, within 2 hours of ending each infusion, and during infusion/s as clinically indicated (See Section 7.5.2)
- Predose blood samples for biomarkers (Cycle 1 only). See time points in Appendix D.
- Predose blood samples for PK (Cycle 1 only). See time points in Appendix D.
- Post dose blood samples for PK (Cycle 1 only). See time points in Appendix D.
- Predose blood samples for ATA (Cycle 1 only). See time points in Appendix D.
- LV infusion (if dosing criteria in Section 5.2.3.5 are met)
- Pembrolizumab infusion
- Collection of concomitant medication information
- Collection of AEs

6.3.3.2. Day 3 (Cycle 1 only; required for patients in US sites, optional for patients outside US sites; window: Days 3-4)

Blood samples for PK

6.3.3.3. Day 8

- Pre-dose
 - Serum chemistry panel (detailed in Section 7.5.3) to be evaluated prior to infusion (Cycles 1 and 2 only).
 - CBC with differential (-2-day window; detailed in Section 7.5.3) to be evaluated prior to infusion.
 - Blood samples for PK assessment (Cycle 1 only; see Appendix D)
- Vital signs (within 60 minutes prior to LV infusion, within 2 hours of ending of infusion, and during infusion as clinically indicated. See Section 7.5.2)
- LV infusion
- Post-dose
 - Cycle 1 only: blood samples for PK assessment (Appendix D)

6.3.3.4. Day 15

Part C

- Pre-dose
 - Serum chemistry panel (detailed in Section 7.5.3) to be evaluated prior to infusion (Cycles 1 and 2 only).

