APPENDIX M: MODIFIED TOXICITY PROBABILITY INTERVAL DESIGN SIMULATION REPORT

Introduction

Part C of this study evaluates weekly (q1wk) LV dosing (Day 1, Day 8, and Day 15 of every 3-week cycle). The primary objective of Part C is to evaluate the safety, tolerability, and identify the recommended dose of LV. Toxicity is measured by dose-limiting toxicities (DLTs) observed within the first cycle. Dose escalation in Part C will be conducted according to a modified toxicity probability interval method (mTPI).

DOSE ESCALATION

Overview

There will be 2 selected dose levels for LV in Part C. Intermediate doses of LV may also be evaluated during the execution phase at the discretion of the sponsor upon recommendation by the Safety Monitoring Committee (SMC).

The starting dose level of LV is 1.0 mg/kg. Dose escalation is conducted according to an mTPI method and according to a set of rules governing entry into the study and assignment of dose level. Decisions are described in Section 3.1.3 of the study protocol and detailed in this appendix. They are based on the posterior distribution of the DLT rate and derived independently for each dose level. The trial is closely monitored for safety and for identification of the MTD. If the SMC recommends exploration of an intermediate dose level, an additional dose level may be added.

Modified Toxicity Probability Interval Method

Dose escalation is conducted using the modified toxicity probability interval method. The implementation programs are available at: https://udesign.laiyaconsulting.com/.

For each dose level, i, the probability of a DLT on dose i is denoted by pi. The target toxicity probability in this study is defined as 25%, with a 5% margin. The equivalence interval is [20%, 30%], which contains the doses close to the true target DLT rate that physicians would deem acceptable for treating future patients. The equivalence interval partitions the unit interval (0, 1) into 3 subintervals: (0, 20%), [20%, 30%], and (30%, 1). Doses in these 3 intervals correspond to:

- Under dosing: pi <20%
- Proper dosing: 20% ≤ pi ≤30%
- Over dosing: pi >30%

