At the end of the trial when the toxicity outcomes of all the enrolled DLT-evaluable patients are observed, a dose will be selected as the estimated MTD. The estimation is separated from the design for dose finding. The MTD is selected by performing an isotonic regression that borrows strength across doses. Let $\hat{p}i$ be the posterior mean of DLT rate. The pooled adjacent violators algorithm (PAVA) is applied on $\hat{p}i$ so that the resulting transformed values $\hat{p}i^*$ increase with the

a Dose will be de-escalated if the first 2 DLT-evaluable patients in a dose level experience DLT. Further evaluation of that dose level may be allowed if recommended by the SMC.

dose levels. That is, $\hat{p}i^* \le \hat{p}i+1^*$ for all i. The recommended MTD is the highest dose with a toxicity probability $\hat{p}i^*$ less than or equal to the target DLT rate 25%, i.e.,

Estimated MTD = max $\{i: \hat{p}i \le 25\%\}$

Dose-Escalation Rules

- 1. Dose escalation begins with patient enrollment to dose level of 1.0 mg/kg. At least 2 DLT-evaluable patients per dose level are required to escalate at any dose level. Once all patients in the previous cohort have completed DLT evaluation, patients can be enrolled to the next dose-level cohort. Subsequent enrollment and dose selection occurs via the following rules:
- If a dose level i is unacceptable, de-escalate to the lower dose level and never treat future
 patients at level i. If i = 1, stop the trial and conclude no dose is safe.

Interim Monitoring

The dose escalation will be closely monitored for safety and for identification of the MTD. If no doses are safe, dose escalation for that population will stop, and no MTD will be declared.

Safety Monitoring

If no doses are safe, dose escalation will stop, and no MTD will be declared. Formally, if

[figure not shown]
Pr(pi >25%) >95% for all i

Identification of the MTD

After each dose-level cohort, the estimation of MTD will be performed. If the model's next recommended dose is the same or below the MTD, the dose escalation may be stopped and MTD can be declared. Alternatively, if the model's next recommended dose is above the estimated MTD level, and patients have already been treated at the higher dose level, and the observed DLT rate at the recommended higher dose level exceeds the target DLT rate of 25%, the dose escalation may also be stopped and MTD can be declared.

Simulation Studies

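### Part C lists a Cycle 2 delay DLT that is first met on Day 37, but escalation and expansion turn on a DLT evaluation period stated as 21 days

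*Protocol*

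**What the plan says.** Protocol Section 3.1.5.2 includes in the Part C DLT list: "Prolonged delay (>2 weeks) in initiating Cycle 2 due to treatment-related toxicity". The same section closes with a rule on evaluability: "Patients who do not complete the 21-day DLT evaluation period for reasons other than DLT will not be considered for dose-escalation decisions".

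Other places describe the period as follows:

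- Section 3.1.5: "The DLT-evaluation period is the first treatment cycle in Part A and Part C dose escalation".
- Synopsis, Statistical Methods: the DLT-evaluable set requires follow-up for the full evaluation period, which is glossed as Cycle 1.
- Appendix M, Introduction: "Toxicity is measured by dose-limiting toxicities (DLTs) observed within the first cycle".
- Section 3.1.1, for Part A only: "DLTs will be assessed in the first treatment cycle, through Cycle 2 Day 1".

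Three rules use the outcome. Appendix M (Dose-Escalation Rules) states: "Once all patients in the previous cohort have completed DLT evaluation, patients can be enrolled to the next dose-level cohort". Section 3.1.3.1 and Table 2 escalate on 0 of 2 DLTs and add 4 patients on 1 of 2. Section 3.1.3.2 allows expansion at any dose level that has cleared DLT evaluation.

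Section 5.2.5.2 lets the start of a Part C cycle slip by up to 14 days, and longer with the medical monitor's approval. The protocol therefore expects some patients to be on hold after Day 22.

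**The concern.** A listed DLT should be observable before the plan treats a patient as having finished DLT evaluation. Here one criterion needs about two weeks more than the stated period allows. If a patient's Cycle 2 is on hold for treatment-related toxicity on Day 22, the 21 days are complete and the delay criterion is not yet met. Nothing in the text says that such a patient remains unresolved or that a decision using that patient waits.

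With cohorts of 2, a single DLT changes the decision. What is at stake is the step from 1.0 to 1.25 mg/kg and the opening of expansion, in which up to about 60 patients are planned. The reported count is also affected, because DLT incidence is a primary safety endpoint.

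**Working it through.** **1. Calendar.** Inputs: 21-day cycles (Section 6.3.3) and a delay of more than 14 days (Section 3.1.5.2).

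- Cycle 2 Day 1 is due on Day 21 + 1 = Day 22.
- A delay of exactly 14 days falls on Day 22 + 14 = Day 36.
- A delay of more than 14 days is first true on Day 22 + 15 = Day 37.
- Gap: 37 − 21 = 16 days from the end of the 21-day period, or 37 − 22 = 15 days from the scheduled Cycle 2 Day 1.

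Under the 21-day definition, the criterion cannot be met inside the period.

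**2. The plan's own decisions at n = 2.** Appendix M uses a Beta(1 + x, 1 + n − x) posterior and UPM = Pr(interval)/length on (0, 0.20), [0.20, 0.30] and (0.30, 1).

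| DLTs | UPM escalate | UPM stay | UPM de-escalate | Table 2 |
|---|---|---|---|---|
| 0/2 | 0.488/0.2 = 2.44 | 0.169/0.1 = 1.69 | 0.343/0.7 = 0.49 | E |
| 1/2 | 0.104/0.2 = 0.52 | 0.112/0.1 = 1.12 | 0.784/0.7 = 1.12 | S |

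0/2 reproduces as escalate. 1/2 is an exact tie between stay and de-escalate, printed as stay. One further DLT therefore moves a cohort off escalation. In a cohort of 6, it moves the printed decision from E at 1/6 to S at 2/6.

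**3. What other criteria already catch.** Section 3.1.5.2 also counts failure to receive all three LV doses because dosing criteria are not met. Section 5.2.3.5 requires a neutrophil count of at least 1000/µL on Days 8 and 15 in Part C. Neutropenia that costs a Day 8 or Day 15 dose is thus a DLT within the period. So are febrile neutropenia of Grade 3 or higher, Grade 4 thrombocytopenia, Grade 4 anemia unrelated to underlying disease, and discontinuation in Cycle 1 for treatment-related toxicity. What remains is toxicity that meets none of these and still holds Cycle 2 for more than 14 days, mainly toxicity arising after the Day 15 dose.

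**4. Illustrative size.** The documents give no rate, so both inputs below are assumptions.

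- Let q be the share of patients whose only DLT is the delay. P(at least one in 2) = 1 − (1 − q)². For q = 5% this is 1 − 0.95² = 9.8%. For q = 10% it is 1 − 0.90² = 19%.
- Let p be the true DLT rate and s the share of DLTs that appear only after the period. P(0/2 seen) = (1 − p(1 − s))².

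| p | s = 0 (all counted) | s = 10% | s = 20% | s = 50% |
|---|---|---|---|---|
| 25% | 0.563 | 0.601 | 0.640 | 0.766 |
| 40% | 0.360 | 0.410 | 0.462 | 0.640 |

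Given step 3, the larger values of s are upper illustrations, not expectations.

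**The case against.** The best defense is that the first cycle lasts until Cycle 2 actually starts. Section 5.2.5.2 allows a cycle start to slip, the 21-day sentence deals with patients who drop out for reasons other than DLT, and completing DLT evaluation could mean that every listed criterion has been assessed. On that reading there is no gap. If Cycle 2 Day 1 means the actual start day, the Part A wording also covers the delay. This reading is possible, but Section 3.1.5.2 gives the Part C period a length of 21 days, and only Part A has the wording about Cycle 2 Day 1. If the longer period was meant, the Part C text does not say so.

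Safeguards exist. The SMC evaluates each cohort and reviews events after the DLT window, and the sponsor may override the model for safety (Section 3.1.3.1). The recommended dose rests on the totality of data. These limit the consequences, but they are discretionary and are not tied to the DLT count or to a hold on escalation.

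The documents do not support three stronger inferences that a reader might draw:

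- *The delay criterion is the only way prolonged marrow toxicity becomes a DLT.* Step 3 of the working shows several others.
- *The neutropenia reported after three weekly doses shows that such delays will be common.* Section 3.2.3.4 reports this at 1.5 mg/kg, which is not a planned Part C dose, and does not name the cycle. Sections 3.2.3.2 and 3.2.3.4 report no DLTs with weekly monotherapy at 1.0 and 1.25 mg/kg.
- *The Part C DLT rate or MTD is biased low.* No text says that a patient on hold is scored as DLT-free, and Appendix M estimates the MTD once the outcomes of all DLT-evaluable patients are observed. The text permits a premature decision. It does not show that one occurred.

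**Conclusion.** The concern holds as a conflict between stated rules. Part C lists a DLT first met on Day 37, gives a 21-day evaluation period, and makes escalation and expansion depend on completing that evaluation. A 2-patient cohort can be treated as 0/2 when a delay that later passes 14 days would make it 1/2.

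The likely effect is modest. It is confined to toxicity that meets no other Cycle 1 criterion, and to one planned escalation step plus the opening of expansion. The figure of 10% to 19% of 2-patient cohorts depends wholly on the assumed 5% to 10% of patients. A delay that resolves within 14 days changes nothing.

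**What to change.** Reconcile the Synopsis (Statistical Methods), Sections 3.1.1, 3.1.5 and 3.1.5.2, and Appendix M (Introduction and Dose-Escalation Rules). The DLT criteria, the evaluation period, and the point at which a patient counts as having completed DLT evaluation should agree. Which clinical rule applies is the sponsor's decision. The agreed definition should also reach the SAP: Section 5.1 includes Part C dose finding in the DLT analysis, but the DLT-evaluable set in Section 4.3 covers Part A only.

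If Part C escalation is already complete, the study report should state how Cycle 2 delays were scored and whether any escalation or expansion decision preceded their resolution.

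The cost is wording, plus a short statement in the report. Any effect on decision timing depends on the rule the sponsor adopts.
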